#### 6.2.4 Follow-up Visits

None

#### 6.2.5 Completion/Final Evaluation

The outpatient visit at the time of enrollment is the participant's first and at the same time final visit with regard to the study.

After obtaining the baseline data the research assistant will hand the participant a tablet containing, depending on the group attribution, either the app (App Group) or white noise (Control Group) and will be shown how to operate the tablet.

Participant will then return to the clinic waiting area with the tablet and wait for their regularly scheduled appointment. The patient will be at liberty to when and for how long to listen.

At the end of the waiting room period the participant will be queried again for their levels of pain and anxiety.

After the participant enters the treatment room, he or she will be able to continue to listen to the app or white noise on the tablet. The treating dental practitioner will not be made aware of the group attribution and conduct the treatment as usual. The research assistant will ask the participant every  $10 \min{(+/-2 \text{ minutes})}$  to indicate their pain and anxiety levels. The research assistant will note the duration of chair time, the amount of lidocaine given, if any or which other medications were given during the appointment, and whether the dental practitioner prescribed opioid, prescription or non-prescription drugs at the end of the visit. This information will be obtained by the research assistant from the standard of care provider at the end of treatment.

Before leaving home, the participant will be asked to fill out a satisfaction survey based on a modified Press Ganey Template. The participant will then receive a diary card on which to note pain, average and maximal pain as well its location, use of non-prescription, prescription, and opiate drugs, use of the app, and be provided prestamped envelopes. Patients will be asked to complete the diary daily before bedtime for 7 days. Patients in the experimental group will receive a coupon (coded by group) for free download of the app at the end of their study visit.

Once the diary is mailed back and received by the study team, the participant will be sent a check in the mail. Participants randomized to the control condition will also receive a coupon for the app upon returning the diary.

Participants who discontinue the study intervention early do not require any specific evaluation or follow-up. Potential reasons for early termination may be that patient's dental treatment is cancelled by the treating clinician or that the patient doesn't want to be bothered to provide more data. Since this study is on an intent-to-treat all study

data that are already collected will be maintained and the total patient enrollment numbers will form the denominator of analyses.

#### 7. SAFETY ASSESSMENTS

The app is a non-Significant Risk Device (NSR). It does not perform diagnostic tasks or tie in with a device that requires FDA clearance (such as apps aiding in ECG interpretation or detection of skin malignancies). The NSR status was confirmed by the Tufts IRB approval letter of 7/20/2017.

## 7.1 Specification of Safety Parameters

Expected risks to the subject are as follows:

The risks of participating in this study are not beyond the normal risks for the dental procedures in the TUSDM Craniofacial Pain Center which are considered standard of care.

Patients who are randomized to one of the control group and who are anxious may be disappointed for not getting the app while waiting.

There is the risk of loss of confidentiality to the subject by participating in this study. This risk will be kept to a minimum by following procedures listed under the confidentiality section of the TUSDM IRB.

These risks are considered to be minimal and are addressed in the protocol and consent form.

Because any dental procedure with or without the app can cause increasing anxiety and pain, anxiety and pain will be monitored at frequent intervals with validated 0-10 verbal assessment scales during their clinic visit. The investigators at the Craniofacial Pain Center at TUSDM are furthermore experts in managing patient's pain and distress and assure (as they do for all their patients) that they leave with acceptable comfort levels. [name] and [name] are furthermore psychologically trained and will be able to recognize any unexpected AEs related to participating in the study.

When patients hear drill sounds or had prior traumatic experiences and the environment suddenly reminds them of those, they can vividly relieve the old trauma. This is very rare in a dental setting and can occur whether patients would listen to an app or not.

# 7.2 Methods and Timing for Assessing, Recording, and Analyzing Safety Parameters

Adverse events will be recorded in source documents and on case report forms. All adverse events and non-serious situations will be recorded, monitored, and reported to the IRB at time of continuing review or at the study's termination if this occurs before the study's next continuing review.

To assess relationship of an event to study intervention, the following guidelines are used:

- 1. Related (Possible, Probable, Definite)
  - i. The event is known to occur with the study intervention.
  - ii. There is a temporal relationship between the intervention and event onset.
  - iii. The event abates when the intervention is discontinued.
  - iv. The event reappears upon a re-challenge with the intervention.
- 2. Not Related (Unlikely, Not Related)
  - i. There is no temporal relationship between the intervention and event onset.
  - ii. An alternate etiology has been established.

#### 7.3 Adverse Events and Serious Adverse Events

## **Adverse Event (AE)**

An adverse event (AE) is any untoward medical occurrence in a human subject, including any abnormal physical exam or laboratory finding, symptom, or disease, temporally associated with a subject's participation in the research.

## **Unanticipated Problems (UP)**

An unanticipated problem is an incident, experience, or outcome that meets all of the following criteria: 1) The nature, severity, or frequency is unexpected for the subject population or research activities as described in the current IRB approved protocol, supporting documents, and the ICF(s); 2) it is related or possibly related to participation in the research; 3) it suggests the research may place the subject or others at a greater risk of harm then was previously recognized.

## **Unanticipated Adverse Device Effects (UADEs)**

Unanticipated adverse device effect means any serious adverse effect on health or safety or any life-threatening problem or death caused by, or associated with, a device, if that effect, problem, or death was not previously identified in nature, severity, or degree of incidence in the investigational plan or application (including a supplementary plan or application), or any other unanticipated serious problem associated with a device that relates to the rights, safety, or welfare of subjects.

## **Serious Adverse Event (SAE)**

A serious adverse event is one that results in death, or is life-threatening, or results in hospitalization or prolongation of existing hospitalization, or results in a persistent or significant disability/incapacitation, or results in a congenital anomaly/birth defect, or may jeopardize the subject's health and may require medical or surgical intervention to prevent one of the other outcomes listed above.

## 7.4 Reporting Procedures

Adverse events will be recorded in source documents and on case report forms. All adverse events and non-serious situations will be recorded, monitored, and reported to the IRB at time of continuing review or at the study's termination if this occurs before the study's next continuing review.

Serious adverse events will be recorded in source documents and on case report forms. Serious Adverse Events that meet the criteria of an unanticipated problem will be reported to the IRB within 5 business days following the Reportable New Information Policy. Serious Adverse Events not meeting the criteria for an unanticipated problem will be reported to the IRB at time of continuing review or at the study's termination if this occurs before the study's next continuing review.

Unanticipated problems will be recorded in source documents and on case report forms. Unanticipated problems will be reported to the IRB within 5 business days after the PI/study team becomes aware of the problem. A Reportable New Information Form will be submitted to the IRB no later than 5 business days after the PI/study team becomes aware of the problem.

UADEs will be documented in source documents and on case report forms as to onset, severity, duration, management, outcome and relatedness to the test device. UADEs will be reported to the IRB within 5 business days after learning of the effect.

## 7.5 Follow-up for Adverse Events

AEs will be followed until resolved or considered stable through the psychologists of the Craniofacial treatment Center at Tufts (Drs. [name], the site PI, and [name], the research assistant).

## 7.6 Safety Monitoring

A Data Safety Monitoring Plan (DSMP) and Independent Monitoring Committee protocol has been submitted to NCCIH on 06/01/2017 and has been approved.

#### 8. INTERVENTION DISCONTINUATION

Subject Withdrawal/Termination Criteria are

- Subjects who do not comply with the study procedures, such as not returning diaries
- Subjects who decide to stop participating in the study will be withdrawn from further data requests.

The Site-Principal Investigator and clinical co-investigators will determine whether subjects (either withdrawn subjects or subjects completing the study) are in need of additional treatment and/or follow-up observation as a result of participation in this trial. Subjects and/or their insurance will be responsible for the cost of any standard of care follow-up visits or additional treatment that is not part of this study.

If a subject withdraws or is withdrawn, any data collected up to that point will still be used for the study which is on an Intent-to-Treat basis and therefore will include the withdrawn individuals in the denominator. However, no further data will be collected for that subject.

#### 9. STATISTICAL CONSIDERATIONS

## 9.1 General Design Issues

This randomized controlled trial is a single-site pilot trial to assist in feasibility assessment and sample size estimation in a pivotal trial to test the hypothesis that listening to a Comfort Talk® app with calmative content reduces pain, anxiety, and post-procedural medication use. The study design is based on a 1:1 randomized attribution of participants to an app or white noise as control condition.

The feasibility criteria are not hypothesis driven and are based on practical pass/fail criteria:

primary feasibility outcome parameter:

• ability to obtain complete on-site data sets from at least 90% of patients enrolled - with at least 40% from patients in the app group and at least 40% from patients in the control group)

secondary feasibility outcome parameters:

- ability to enroll 60 patients by day 150 after initiation of recruitment in the clinic (=day 1)
- obtaining 38 packages of filled out diary cards (at least 16 from patients in the app group and at least 16 from patients in the control group).
- 90% of patients in app group listen to app  $\geq$ 5 min

Since a significant reduction in anxiety in the waiting room is the main ingredient that underlies all other hypothesized effects for Phase II outcomes, even in the face of proven technical feasibility of trial execution, it was chosen as the overall primary objective for Phase II.

Statistical hypotheses for Phase II are:

Providing participants a calmative Comfort Talk® app at the time of their dental outpatient visit

- reduces anxiety in the dental waiting room (primary hypothesis)
- reduces pain in the dental waiting room
- reduces anxiety during dental treatment
- reduces pain during dental treatment
- improves patient satisfaction with the dental visit
- reduces anxiety in the week after treatment
- reduces pain in the week after treatment
- reduces need for opioids and analgesics the week after treatment

The overall premise is that showing patients at the time they experience distress how to cope while they are still under physician/dentist supervision will carry over into recovery and thus reduce need for addictive drugs (see also 2.2).

## 9.2 Sample Size and Randomization

The goal is to enroll 72 patients in a randomized design with 36 patients utilizing the app and 36 patients not utilizing the app. Those randomized to utilizing the app (app group) will receive a tablet with the app, those randomized to not utilizing the app (control group) will receive a tablet with white noise.

Based on prior trial experience, it is likely that 90% of patients on site will provide onsite data sets (primary objective). In two prior trials, in which 241 and 201 patients, respectively, were followed through their invasive medical procedures, all enrolled patients (100%) provided these data (1,3). In a breast-biopsy trial, 4 of 240 (1.6%) withdrew by that stage (2). In these past trials patients received more personal attention through live delivery of the content that is now offered in an app, and thus willingness to remain in the study may not be as high in the current trial but still should exceed 90% for feasibility. To arrive at a reasonable sample size to satisfy this requirement, but also obtain a sense of validity of the primary hypothesis for Phase II and obtain estimates of data distribution, which will be critical for sample size and analysis planning Phase II, we conducted following sample size calculations.

Assuming an average anxiety rating of 4 at the end of the waiting room time without prior guidance in relaxation or app (see Fig 3., time 0), the expectation of improved subsequent outcomes with a 35% reduction in anxiety to 2.6 based on Schupp et al (33 vs 53 on STAI - (1) and a standard deviation of 2, 66 patients would be needed for a two-sided test with a power of 0.80 and an alpha of 0.05.

This degree of reduction in anxiety is clinically significant based on prior work in a clinical trial that demonstrated that a 35% difference in anxiety at the onset of an invasive medical procedure is associated with significant differences in the subsequent experience of pain and anxiety during the procedure, need for opioid analgesics and sedatives, and the overall length of the procedure. These factors directly affect procedure safety and throughput (e.g. economical efficiency).

Using this number of 66 patients as guide to determine a target study size for assessment of the feasibility parameters an enrollment of 72 patients seemed compatible with an early drop-out of 6 patients resulting in an expected 91.7% onsite data return rate. This will also support the expectation of receiving 38 packages of filled out diary cards (53%), a secondary objective. In a prior breast biopsy trial, in which patients collected for 5 days 4 daily salivary cortisol samples, filled out more extensive diary cards, and sent all back to the lab, 36% complied (45). Considering the higher burden of also getting 4 daily salivary samples and 4 daily entries as compared to one daily entry on cards at bed-time a 53% return rate for this pilot is reasonable.

This sample size of 72 participants may also give an estimate in as far results previously achieved with live delivery of Comfort Talk® may be transferable to assumptions for app delivered Comfort Talk® content.

The following sample size estimate supports the evaluation of post-procedure pain and is based on a prior breast biopsy trial (19) during which we collected postoperative pain measures. In that study, postoperative pain ratings in the live Comfort Talk group were less than those of the control group (1.6 vs 3.5) with a standard deviation of 2.0. Assuming a similar reduction in pain from 3.5 to 1.6 on day 1 (similar effect size in a study by from TUSDM) (43) and a standard deviation of 2.0, 38 subjects total would be needed for a two-sided test with a power of 0.80 and an alpha of 0.05. Considering that not everyone will send back their diaries, the target of 72 patients may suffice.

#### **Treatment Assignment Procedures**

Randomization was chosen as it provides the highest level of scientific evidence.

This is a pilot trial with a relatively small number of participants. The randomization codes will not be broken until all statistical analyses having been performed by the statisticians in a blinded fashion.

We will use 4 tablets, 2 with Comfort Talk content, two with white noise, labeled A,B,C,D. The tablets will be preloaded with the respective app content in a randomized sequence at Hypnalgesics, unknown to the Tufts investigators.

[name]/research assistant will consent the patients, hand the patient the tablet based on the randomization scheme (which will be provided by Drs. [name] and [name]), obtain baseline data, query and record trial data but **will not analyze** data. There is a possibility that he may become unblinded, however he will not share his observations with the analyzing team.

Strict blinding will be maintained for the analyzing team. Analysis of data will be performed by the statisticians Drs. [name] and [name], who will remain blinded throughout the trial as to which tablet contained which content. They will not have any patient interactions and thus also will also not be privy to any accidental unblinding of tablet content during the dental treatment.

## 9.3 Definition of Populations

The study is based on ITT (Intent to treat).

## 9.4 Interim Analyses and Stopping Rules

There is no plan for interim analyses.

This study may be terminated for the following reasons:

- Discovery of unforeseen risk that could jeopardize the dental/physical wellbeing of subjects.
- Enrollment or recall rates that are not likely to produce sufficient data for evaluation of safety and efficacy
- Non-compliance with the clinical investigational plan, the Investigator
- Agreement, applicable FDA regulations or conditions of approval imposed by the reviewing IRB
- Any new information becomes available during the trial that necessitates stopping the trial
- Withdrawal of IRB approval

Findings that might trigger a safety review are the number of SAEs overall, the number of occurrences of a particular type of SAE, severe AEs/reactions, or increased frequency of events. Such findings are presented to the Independent Monitoring Committee (IMC) statistician to review the events by group to determine whether there are statistical as well as clinical concerns. The statistician reports his findings to a closed session of the IMC or to the Safety Officer and/or NCCIH. The findings are used to determine what steps will be taken.

#### 9.5 Outcomes

The outcomes are based on patient's reported measures of anxiety, pain, satisfaction rating on a Likert scale, and medication use and objective numbers with regard to the feasibility measures. These data are clear numerical values and not subject to interpretation/adjudication with regard to their reported value.

There will be no loss of follow-up for data for the primary outcome parameter since all patients who are on site are the denominator and any missing data would be reflected in the percentage of complete on-site data sets.

For management of any subsequent missing intermittent data the method will use all data available data that are available within the intent-to-treat overall approach.

We will be using all available data and calculate the percent missing data for each treatment group. The degree of missingness will inform accept/reject feasibility which is defined as complete on-site data sets from at least 90% of patients enrolled with at least 40% from patients in the app group and at least 40% from patients in the control group) and 38 packages of filled out diary cards 52% with at least 16 (22%) from patients in the app group and at least 16 from patients in the control group (22%)

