If the data does not meet the assumptions required for the time-series analysis methods listed above, the time-series data from each patient will be summarized by calculating area under the curve using trapezoidal rule. Normality will be assessed graphically using histograms and q-q plots. Area under the curve will be compared between the two treatment groups using t-test if normally distributed or if normality can be achieved by log-transformation. Mann-Whitney U test will be used if data is non-normal.

Pain and anxiety for the week after the post procedure will be assessed for linearity graphically. Individual patient pain and anxiety slopes will be compared using t-test or Mann-Whitney U test, as appropriate, to determine if the rate of change of pain and anxiety is different between treatment and control groups. In addition, the overall mean pain and mean anxiety for each patient will be calculated and compared between treatment and control groups using t-test or Mann-Whitney U test as appropriate.

Drug usage, converted in equivalence drug score, and satisfaction scores will be assessed by t-test if normally distributed or Mann-Whitney-U test if non-normal.

All tests will be two-sided at a significance level of <0.05. Sample size will be based on results of Phase I assuming a power of 80%. SAS version 9.4 will be used for analysis.

Patients' age, gender, procedure type, and NIDA Quick score will be assessed for their potential as confounding factors. This will support guidance for trial design in Phase II.

The study sample of this pilot is likely underpowered to perform meaningful subanalyses of differences in intervention effect between gender and racial/ethnic subgroups. They will be performed to not miss potentially clinically significant differences as prescribed by NIH policy.

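### With 34 of 72 diaries expected missing, the week-after comparisons are unadjusted tests on returners under an ITT label, and can be biased if who returns differs by arm

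*Combined protocol and SAP*

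**What the plan says.** Section 9.2 sets the enrolment: "The goal is to enroll 72 patients in a randomized design with 36 patients utilizing the app and 36 patients not utilizing the app". On diaries it adds: "This will also support the expectation of receiving 38 packages of filled out diary cards (53%), a secondary objective". Sections 1.2 and 9.5 require at least 16 packages from each arm.

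Section 9.3 defines the population in one sentence, "The study is based on ITT (Intent to treat", and does not say how a patient without a diary enters the analysis. Sections 6.2.5 and 8 keep all enrolled and withdrawn patients in the denominator.

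The missing-data rule in Section 9.5 is "We will be using all available data and calculate the percent missing data for each treatment group". For the week after treatment, Section 9.6 compares individual slopes by t-test or Mann-Whitney test. Averages over the week are treated likewise: "the overall mean pain and mean anxiety for each patient will be calculated and compared between treatment and control groups using t-test". The rank test is again the alternative, and the drug score is tested in the same way.

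Pain and anxiety are rated before the tablet is handed over, at the end of waiting, in the chair and on leaving (Sections 6.2.2 and 9.5.2). None of these ratings enters the week-after comparisons. The factors that Section 9.6 will examine as possible confounders are age, gender, procedure type and NIDA score.

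**The concern.** A mean, slope or drug score cannot be computed without a diary, so the week-after tests compare returners only. Randomisation balances the 36 and 36 who were enrolled. It does not guarantee balance between the roughly half of each arm who post a diary back. The percentage missing by arm shows how many are absent, not which patients they are.

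The design gives a reason why the mix of returners might differ. App patients receive the download coupon at the visit, while control patients receive it only after returning the diary (Précis, Design and Outcomes; Section 6.2.3). The Risks text in Section 2.2 expects that anxious control patients may be disappointed at not having the app. An anxious control patient may therefore have a motive to return that an app patient lacks.

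At stake are the week-after effects on pain, anxiety and drug use, which Section 9.6 intends to use in planning Phase II.

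**Working it through.** **1. The plan's own figures.** Return is 38/72 = 52.8%, so 34/72 = 47.2% are missing. The 38 comes from Section 9.2: "Assuming a similar reduction in pain from 3.5 to 1.6 on day 1", where ratings in the earlier trial "were less than those of the control group (1.6 vs 3.5) with a standard deviation of 2.0". The standardised effect is 1.9/2.0 = 0.95. The normal formula gives 2 × (1.96 + 0.84)² / 0.95² = 17.4, so 18 per arm or 36 in total. The t-based solution is 36.8 in total, so 19 per arm or 38. The figure is reproduced. Power with 38 diaries is 81% at 19:19 and 80% at 16:22, so 38 is both the number needed and the number expected.

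**2. Bias formula.** Let X be the standardised pre-tablet rating, ρ its correlation with the diary outcome, and m the mean of X among returners in an arm. If the treatment effect is constant and return depends only on arm and X:

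bias = ρ × SD × (m_app − m_control)

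SD 2.0 is from Section 9.2. The documents give neither ρ nor the dependence of return on X. I assume ρ = 0.6 and a logistic dependence with the odds ratio (OR) per SD of X shown below; m follows by integrating over a normal X. The multiplier is 0.6 × 2.0 = 1.2. Mean return is 52.8% in each arm except in the second row.

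| Assumed return pattern | Gap in m between arms | Size of bias (points) | Type I error, unadjusted |
|---|---|---|---|
| Same dependence (OR 2), same rate | 0.295 − 0.295 = 0 | 0.00 | about 5% |
| Same OR 2, return 16/36 vs 22/36 | 0.348 − 0.244 = 0.104 | 1.2 × 0.104 = 0.12 (simulated 0.13) | 5–6% |
| Dependence in control only, OR 2.1 | 0.312 − 0 = 0.312 | 1.2 × 0.312 = 0.37 (simulated 0.38) | 9% |
| Opposite dependence, OR 1.6 and 1/1.6 | 0.211 + 0.211 = 0.422 | 1.2 × 0.422 = 0.51 | 12% |

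Type I error is from simulation of 36 per arm with no true effect. As a check, the standard error at 19:19 is 2.0 × √(2/19) = 0.65. The biases of 0.13, 0.38 and 0.51 are then 0.20, 0.58 and 0.78 standard errors, and a shifted normal gives about 5.5%, 8.9% and 12.2%. Against the planned 1.9 points the biases are 7%, 20% and 27%.

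**3. Range.** With OR 2 and ρ from 0.3 to 0.7, the bias is 0.06–0.15 points for the 16 vs 22 split, 0.18–0.41 for dependence in one arm only, and 0.35–0.83 for opposite dependence.

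**4. Effect that varies with baseline.** With equal dependence (OR 2) the returners' mean X is shifted by 0.295 SD. If the effect changes by 0.5 to 1.0 point per SD, the effect in returners differs from that in all randomised patients by 0.295 × 0.5 = 0.15 to 0.295 × 1.0 = 0.30 points.

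**5. After adjustment.** Regressing the diary outcome on arm and X among returners brings every row of the table to within about 0.01 points of zero, with type I error of 4.7–5.2%. Variance falls by about 30% (29–34% across runs). If return depends on the diary outcome itself (opposite dependence, OR 1.6), adjustment reduces the bias only from 0.84 to 0.55 points, about one third. A main-effect covariate also does not recover the all-randomised effect in step 4.

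**The case against.** A reader might infer that the comparison is biased whenever return depends on baseline distress. The documents do not support that. With the same dependence and the same return rate in both arms and a constant effect, the returner groups stay balanced and the bias is zero (first row of the table). Nor does the coupon arrangement show that bias will occur. It gives a motive that differs by arm, while the $25 check rewards return in both. If it changes only return rates, to the most uneven split that still passes at 38 diaries, the bias is about 0.13 points. No section gives a reason for the opposite-dependence row, so that row is an outer illustration.

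The adjusted result of zero is partly built in, since return was generated from the rating used for adjustment.

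Relevance is also limited. Phase I success is judged on sums and percentages, and diary return by arm is itself a criterion. The primary Phase II outcome, waiting-room anxiety, is collected on site and is untouched. Section 9.6 says the analyses may change after Phase I. The ITT wording can be read as analysis regardless of listening and retention of withdrawn patients' data, and Section 9.5 openly says available data.

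All of this stands and sets the size of the point. It does not remove it: nearly half the diaries are expected to be absent, no section says how that is handled beyond counting, and ratings planned for every patient go unused.

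**Conclusion.** The concern holds in a conditional form. The week-after comparisons are unadjusted tests on about 53% of those randomised. They can be biased if return depends on baseline distress differently by arm, if return rates differ by arm together with such dependence, or if the effect varies with baseline distress. Under the assumed values the bias runs from nothing to about 0.5 points on a 0–10 scale, with type I error from 5% to 12%. The odds ratios and the correlation of 0.6 are assumptions; the 47%, the SD of 2.0 and the 1.9-point effect are the plan's.

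Baseline adjustment is worthwhile even if no bias exists, because of the gain in precision. It rests on return being missing at random given arm and the pre-tablet rating, and it is not a full remedy if return follows the diary outcome. This should be changed, but it does not threaten the pilot's primary feasibility result.

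**What to change.** In Section 9.6:

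- Make the week-after pain and anxiety comparisons baseline-adjusted. Use either ANCOVA of the patient's diary mean or a repeated-measures model of the daily ratings, with the pre-tablet rating of the same measure as covariate. Name a rank-based or ordinal version for skewed data.
- Adjust the drug-score comparison for pre-tablet pain and anxiety; a model of ratings alone does nothing for this outcome.
- Tabulate baseline and on-site ratings of returners and non-returners by arm.
- State the missing-at-random assumption, and describe the unadjusted t-test as a returners-only analysis rather than ITT.

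Pooling on-site and diary ratings in one model is optional. It would mix momentary spoken ratings with bedtime diary entries, and it was not tested here.

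The cost is a few sentences in the SAP and a little more analysis in the SAS already planned, with no new data.
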